1.2 Sample Size

For the primary efficacy endpoint of stable vision (ie, patients who lose fewer than 15 letters in BCVA from baseline) at Week 52, a sample size of 240 patients in each treatment group will provide approximately 95% power with a 2-sided alpha level of 0.05 to demonstrate non-inferiority of an abicipar group versus ranibizumab with a non-inferiority margin of 10%. This calculation is based on the assumption of a 90% response rate for both groups. With an anticipated dropout rate of approximately 20% during a 52-week period, a total of 900 patients will be enrolled so that approximately 720 patients (240 per group) will complete 52 weeks as required for the primary endpoint evaluation.

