2.1 Analysis Populations

The following 3 populations will be used for statistical analysis: intent-to-treat (ITT), perprotocol (PP), and safety.

The ITT population includes all randomized patients. The ITT population will be used for all efficacy analyses.

The PP population includes all randomized and treated patients who do not have protocol deviations that impact the primary efficacy variable. The PP population will be used for analyses of the primary and secondary efficacy variables. Primary considerations for PP definition include treatment compliance that would represent the intended regimen adequately.

Specifically, the PP population will include patients who

- 1. Received at least 9 study treatments (including sham) and attended at least 9 scheduled monthly visits during the first year (before the Week 52 visit), and;
- 2. Had not missed 3 or more consecutive study treatments (including sham) before the 9th study treatment, and;

3. Did not have any major protocol deviations that impacted efficacy outcomes prior to the Week 52 visit

The PP population will also include patients who discontinued from the study as a result of treatment failure without a major deviation prior to Week 52 that impacted efficacy outcomes (even if they met criteria #1 or #2 above). Patients who escaped to standard of care by meeting the protocol criteria before Week 52 and study exit are considered as treatment failures. Final determination of the PP population will be made based on masked review of the data. Detailed specification will be documented separately prior to the primary database lock.

The safety population includes all treated patients and will be used for all safety analyses.

Analyses for ITT and PP populations will be based on randomized treatment group, whereas analyses for safety populations will be as treated, ie, based on the actual treatment that the patient received.

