5.2 Primary Efficacy Analyses

The primary efficacy endpoint is the proportion of patients with stable vision at Week 52, defined as vision loss of fewer than 15 letters in BCVA from baseline. Patients who escaped to standard of care by meeting the protocol criteria will be set to failures for the primary endpoint of stable vision at Week 52. Confirmation for meeting the protocol criteria is based on the marked reasons captured on the Standard of Care eCRF, which states: "Loss of \geq 30 letters in BCVA from baseline (in any post-baseline visit), and persistent fluid (subretinal and intraretinal) by OCT, judged to be the cause of the BCVA loss (not explained by reasons other than the progression of neovascular AMD)."

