Tipping point analysis as described in Section 5.2.4.2 will be performed for BCVA change using the PP population. The tipping region will be constructed based on the combinations of values for δ_{2Q8} , δ_{2Q12} , or δ_{rQ4} that resulted in a lower bound of the 95.1% CI for the difference of abicipar (2Q8 or 2Q12) minus ranibizumab less than -5 letters.

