No interim analyses are planned for this study. However, an independent DSMC will assess the unmasked safety data during the study. To preserve an overall alpha of 0.05 for the study, an adjustment of 0.001 will be made and an alpha level of 0.049 will be used for testing purposes. Therefore, 95.1% confidence intervals will be constructed for the primary efficacy analysis.

Statistical Analysis Plan for 150998-005 CSR (Amendment 2)

11. Deviations from Protocol

There are no deviations from the current study protocol.

12. References

Yan X. and Su X.G Stratified Wilson and Newcombe confidence intervals for multiple binomial proportions. Statistics in Biopharmaceutical Research. 2010;2(3):329-335.

13. Amendment(s)

13.1 Amendment 1

The following changes were made in Amendment 1:

13.2 Amendment 2

The following changes are made in Amendment 2:

- For Japan Pharmaceuticals and Medical Devices Agency (PMDA) review, clarified the gatekeeping procedure for multiplicity adjustment to be applied to statistical tests of secondary efficacy variables (Section 10)

14. Appendix A

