Appendix A: Modified Wald Confidence Interval with Stratifications

Single Imputation (LOCF)

Let i=1, 2, ..., k index strata and let p_{1i} and p_{2i} denote stratum-specific response rates for treatment 1 and 2 in stratum *i*, respectively. Let $d_i = p_{1i} - p_{2i}$, where $p_{1i} = \frac{x_{1i}}{n_{1i}}$, with x_{1i} being the number of responders and n_{1i} being the sample size for treatment 1 in stratum *i*. Similar definition for $p_{2i} = \frac{x_{2i}}{n_{2i}}$.

Let
$$p_{1i}^* = \frac{x_{1i}+2}{n_{1i}+4}$$
 and $p_{2i}^* = \frac{x_{2i}+2}{n_{2i}+4}$

With corresponding variance,

$$v_{1i} = \frac{p_{1i}^*(1-p_{1i}^*)}{n_{1i}}$$
 and $v_{2i} = \frac{p_{2i}^*(1-p_{2i}^*)}{n_{2i}}$

And the variance for the difference in response rates between treatment groups in stratum *i*,

$$v_i = v_{1i} + v_{2i}$$

Define weight $w_i = \frac{n_{1i} * n_{2i}}{n_{1i} + n_{2i}}$

The weighted difference,

$$d = \frac{\sum_{i=1}^{k} w_i d_i}{\sum_{i=1}^{k} w_i}$$

And the variance for the weighted difference is,

$$v(d) = \frac{\sum_{i=1}^{k} w_i^2 v_i}{\left(\sum_{i=1}^{k} w_i\right)^2}$$

The Wald confidence interval for the weighted difference is,

$$d\pm Z_{1-\alpha/2}*\sqrt{\upsilon(d)}$$

where $Z_{1-\alpha/2}$ is the critical value corresponding to the 1- $\alpha/2$ quantile of the standard normal distribution.

Multiple Imputation

Let $V_{(j)}$ denote the variance V(d) for the point estimate from the j^{th} imputed dataset.

Hence, the within-imputation variance over all imputed data can be calculated as following:

$$\bar{V} = \frac{1}{m} \sum_{j=1}^{m} V_{(j)}$$

And the between-imputation variance is $B = \frac{1}{m} \sum_{j=1}^{m} (d_{(j)} - \bar{d})^2$

Where $d_{(j)}$ is the weighted difference for the j^{th} imputation invocation and \bar{d} is the average of weighted differences over all imputation invocations.

The total variance is the combination of within- and between-imputation variance:

$$T = \bar{V} + \left(1 + \frac{1}{m}\right)B$$

For SAS application, plugging in *d* as the MODELEFFECTS and $\sqrt{V(d)}$ as the STDERR for PROC MIANALYZE.

The lower bound of the confidence interval is,

$$LB = \bar{d} - Z_{1-\alpha/2} * \sqrt{T}$$

and the upper bound of the confidence interval is,

$$UB = \bar{d} + Z_{1-\alpha/2} * \sqrt{T}$$

where T is the total variance from imputed data.

IOP is not assessed at 5-min postinjection; only 20 min postinjection

ALLERGAN

Statistical Analysis Plan for AMD P3 CEDAR Amendment 2

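### SAP Appendix A: the multiple-imputation interval uses divisor m and a normal quantile, so it is slightly narrower than Rubin's rules give; the effect is minor unless m is small

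*SAP*

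**What the plan says.** The Multiple Imputation part of SAP Appendix A averages the per-imputation variances to get V̄. It then defines the spread between imputations with divisor m: "And the between-imputation variance is $B = \frac{1}{m} \sum_{j=1}^{m", the summand being the squared deviation of each imputed difference from their mean. The total is T = V̄ + (1+1/m)B. The lower limit is "LB = \bar{d} - Z_{1-\alpha/2} * \sqrt{T" with the root closed after T, and the upper limit mirrors it. Z is defined earlier in the appendix as a standard normal quantile, and no degrees of freedom are given.

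Between T and the limits, the appendix says to pass d and √V(d) to PROC MIANALYZE. After the limits it adds "where T is the total variance from imputed data".

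Multiple imputation is a sensitivity analysis (Protocol 7.3.1); the primary analysis uses LOCF (SAP 5.2.2). SAP Section 9 says that "an alpha level of 0.049 will be used for testing purposes". SAP 5.3.1 refers to a further section on sensitivity methods ("Tipping point analysis as described in Section 5.2.4.2 will be performed for BCVA change using the PP population"). That section is not in the text available, so no omission of m, or of which interval will be reported, is alleged here.

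**The concern.** The (1+1/m) factor allows for using a finite number of imputations. It does so only if B is an unbiased estimate of the between-imputation variance, which needs divisor m−1. With divisor m the allowance disappears. Replacing t by Z also drops the allowance for estimating B from only m values. Both departures narrow the interval.

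In a non-inferiority trial a narrower interval errs towards declaring success. The interval supports the missing-data check on the primary endpoint, so at small m it could sometimes clear −10% when Rubin's interval would not.

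**Working it through.** **The plan's own figures.** The documents give no numerical result for this interval. The inputs around it reproduce:
- Alpha: 0.05 − 10 × 0.0001 = 0.049, so z(0.9755) = 1.9686.
- Power at 240 per group, 90% in both groups, margin 10%: SE = √(0.18/240) = 2.74 points, which gives 95.46% at alpha 0.05 and 95.38% at 0.049 (the SAP says about 95%).
- Enrolment: 720/0.80 = 900.

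**Step 1, the divisor.** The sum of squared deviations averages (m−1) times the true between-imputation variance. The printed B therefore averages (m−1)/m of it, and (1+1/m)B averages (m+1)(m−1)/m² = 1 − 1/m² of it. Rubin's rules give 1 + 1/m.

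| m | printed | Rubin |
|---|---|---|
| 5 | 0.96 | 1.20 |
| 10 | 0.99 | 1.10 |
| 20 | 0.9975 | 1.05 |

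**Step 2, the half-width.** Set V̄ = 1 and let g be the fraction of missing information, (1+1/m)B/T with B on m−1. Then:
- T = 1/(1−g)
- T as printed = 1 + (T−1)(m−1)/m
- df = (m−1)/g²
- Shortfall as printed = 1 − z√(T as printed)/(t√T)
- Shortfall if only Z is wrong = 1 − z/t

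Worked case, m=5 and g=0.20: T = 1.25, T as printed = 1.20, df = 100, t = 1.993. The divisor alone costs 1 − √(1.20/1.25) = 2.0%. Z alone costs 1 − 1.9686/1.993 = 1.2%. Together they cost 3.2%.

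Half-width shortfall against Rubin's rules, same V̄:

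| m | printed, g = 5% / 10% / 20% | Z only, g = 5% / 10% / 20% |
|---|---|---|
| 5 | 0.6% / 1.3% / 3.2% | 0.08% / 0.3% / 1.2% |
| 10 | 0.3% / 0.6% / 1.5% | 0.03% / 0.14% / 0.5% |
| 20 | 0.14% / 0.3% / 0.8% | 0.02% / 0.06% / 0.26% |
| 100 | 0.03% / 0.06% / 0.15% | below 0.05% throughout |

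The Z-only columns cover the reading in which software supplies T with divisor m−1 and the printed limits are then applied.

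**Step 3, the offset.** Appendix A computes the variance from (x+2)/(n+4). With 150 per stratum this widens the complete-data SE by 4.5% at 90% vs 90% (2.56 against 2.45 points) and by 2.5% at 80% vs 90%.

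**Step 4, error rates.** These are simulated with assumed inputs: two equal strata, 300 per arm, values missing at random, imputation from a Beta(x+0.5, n−x+0.5) posterior without BCVA history, the Appendix A variance, and 200,000 runs per cell. The Monte Carlo SE is 0.035 points at 2.45%.

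False non-inferiority at 80% vs 90%, nominal 2.45%:

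| values missing | m | printed | Z only | Rubin |
|---|---|---|---|---|
| 10% | 5 | 2.49 | 2.37 | 2.33 |
| 10% | 10 | 2.44 | 2.38 | 2.37 |
| 10% | 20 | 2.40 | 2.37 | 2.37 |
| 20% | 5 | 2.80 | 2.56 | 2.41 |
| 20% | 10 | 2.54 | 2.44 | 2.37 |
| 20% | 20 | 2.49 | 2.44 | 2.41 |

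At 5% missing, all cells lie between 2.28 and 2.37.

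Runs at 90% vs 90% that clear −10% when Rubin's interval does not (printed / Z only):
- 20% missing: m=5, 1.2% / 0.6%; m=10, 0.44% / 0.18%; m=20, 0.17% / 0.06%.
- 10% missing: m=5, 0.30% / 0.10%; m=20, 0.05% / 0.01%.
- 240 per arm, 20% missing: m=5, 1.88% / 0.96%; m=20, 0.31% / 0.13%.

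Step 2 fixes missing information, whereas Step 4 fixes the share of values missing. At 20% of values missing, the information fraction averages about 0.20 but varies between runs. The simulated mean half-widths at m=5 (5.54 printed against 5.77 points) therefore imply 4.0%, not exactly 3.2%.

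**The case against.** The strongest case on the other side is that little follows from the error. From m=10 upward, at up to 20% missing, the printed formula keeps false non-inferiority between 2.28% and 2.54%. In some cells it is closer to 2.45% than the corrected interval (10% missing, m=10: 2.44 against 2.37). The +2/+4 variance belongs to the same procedure, and with it the interval roughly holds its stated level. That stands, and it limits the finding to a minor one. But the offset is incidental: it does not depend on m or on the amount of missing data, and it does not make the pooling formula right.

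Second, the appendix names PROC MIANALYZE, so the printed B may never be coded. If the software divides by m−1, which the documents do not state, only Z against t remains: at most about 0.5% of half-width at m=10 or more. This also stands. But the Z limits are printed after that instruction. If the procedure's own interval is meant and it follows Rubin's rules, the printed limits do not describe it.

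Third, m may be large and stated in text not available. At m=100 the effect is negligible, but the formula would still need correcting.

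**Conclusion.** The formula is wrong as written and the consequence is minor. The direction is algebraic: for B > 0, any finite m and the same V̄, the printed interval is narrower than Rubin's. The size depends on m and on the missing information, neither of which the available text fixes. From m=10 upward the half-width shortfall is about 1.5% or less at up to 20% missing information. The clearest excess, 2.80% false non-inferiority, needs both m=5 and 20% of values missing.

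That 20% is a high case. It matches the plan's expectation ("With an anticipated dropout rate of approximately 20% during a 52-week period"), but two rules would probably lower the share imputed in the per-protocol set. One is the attendance rule: "Received at least 9 study treatments (including sham) and attended at least 9 scheduled monthly visits during the first year". The other is the escape rule: "Patients who escaped to standard of care by meeting the protocol criteria will be set to failures for the primary endpoint".

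The primary LOCF test, the sample size and the alpha allocation are unaffected. The error rates rest on the simulation inputs listed above.

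**What to change.** In the Multiple Imputation part of Appendix A:
- Define B with 1/(m−1).
- In both limits replace Z by the t quantile at 1−α/2, with α = 0.049.
- Add the degrees of freedom: (m−1)[1 + V̄/((1+1/m)B)]².

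The +2/+4 variance can stay. The printed limits are then Rubin's, whether T is coded by hand or taken from software that divides by m−1.

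The edit is one divisor, one quantile and one added line. The sensitivity interval becomes slightly wider. At 90% vs 90%, 300 per arm and 20% missing, the chance that it clears −10% changes as follows:

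| m | printed | Z only | corrected |
|---|---|---|---|
| 5 | 94.2% | 93.6% | 93.0% |
| 10 | 94.3% | 94.1% | 93.9% |
| 20 | 94.5% | 94.4% | 94.3% |
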